13. APPENDICES

13.1. Appendix 1: Protocol Deviation Management and Definitions for Per Protocol Population

13.1.1. Exclusions from Per Protocol Population

A participant meeting any of the following criteria will be excluded from the Per Protocol population:

Number	Exclusion Description
1	Participant who deviated from any inclusion/exclusion criteria
2	Participant who did not receive correct treatment which the participant was randomized to
3	Participant who have missed at least one dose of GSK3640254
4	Participant who did not have Visit 6 HIV-RNA measurement
5	Not withdrawn after meeting the following stopping criteria 
 • Liver chemistry stopping criteria • QTc stopping criteria • Stopping criteria based on Laboratory Abnormality and Adverse Event
6	Informed Consent 
 • Study-specific assessments conducted prior to obtaining proper consent.
7	Study visits performed out of window 
 • Consecutive participant study visits performed out of window • Multiple study visits performed out of window by various Participants (Trending)
8	Incorrect study treatment 
 • Unresolved IP accountability discrepancy • IP storage guidelines not followed • IP incorrectly administered • IP accountability not done
9	Lack of PI oversight
10	Participant Used prohibited medication
11	Participant became pregnant while on study
12	Safety assessments not performed when clinically relevant 
 • Central safety lab samples not collected and/or not properly sent to Q2 when clinically relevant

CONFIDENTIAL

208132

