10.1.3. Population of Interest

The primary pharmacodynamics analyses will be based on the PP population, unless otherwise specified.

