13.11.11. Pharmacodynamic Tables

Pharmacodynamic: Tables					
No.	Population	IDSL / Example Shell	Title	Programming Notes	Deliverable [Priority]
PD Linear and Emax Models					
5.1.	PP	PD_T1	Summary of Estimates from Dose-Response Model	Only include visits from Day 1 to Day 8 for the HIV-RNA change. Part 1 and Part 2 doses all included in the statistical mode.	SAC

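### The per-protocol exclusion list contains items that say nothing about a participant's dosing or HIV-1 RNA, and the dose-response model has no other analysis population

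*SAP*

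**What the plan says.** SAP 13.1.1 opens with a mandatory rule: "A participant meeting any of the following criteria will be excluded from the Per Protocol population". Twelve numbered items follow. Most describe one participant, such as an eligibility breach, wrong treatment, a missed dose, no Visit 6 HIV-1 RNA or a prohibited drug. Others do not:

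- Item 7, second bullet: "Multiple study visits performed out of window by various Participants (Trending". The first bullet already covers consecutive out-of-window visits.
- Item 9: "Lack of PI oversight", with no further definition.
- Item 12: safety assessments, or central safety samples, missed when clinically relevant.
- Item 8 lists "IP accountability not done" beside wrong storage, wrong administration and unresolved discrepancies.

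For the dose-response model, SAP 10.1.3 states: "The primary pharmacodynamics analyses will be based on the PP population, unless otherwise specified". Table 5.1, "Summary of Estimates from Dose-Response Model", is assigned to PP, as are Figure 5.1 and Listing 55. No ITT counterpart is listed. SAP 4 admits a participant to the PK/PD population only if the PP criteria are met, so the exposure-response model inherits the same list. The primary HIV-1 RNA analyses use ITT and are repeated on PP only if the two sets differ.

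**The concern.** A per-protocol set usually supports a main analysis run on everyone treated. Here it is the sole set for the model that pools all five doses. Protocol 3.1 says the study will inform Phase 2b dose selection, and Protocol 10.3.2.2 says both parts together are to describe the full dose-exposure-response curve. The ITT models in SAP 7.1.3.1 cannot stand in: they are fitted part by part, with dose as a class effect.

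Two things are at stake. First, a participant who took every dose and has all the RNA values the model needs can be lost because of a monitoring finding, at a cost in precision and no gain in validity. Second, no rule says whom a trend or oversight finding removes, so two analysts could build different PP sets from the same data.

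**Working it through.** **Which items bear on the model.** The dose-response model needs the dose taken and HIV-1 RNA from baseline to Day 8 (SAP 10.1, 10.1.4).

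| Item in SAP 13.1.1 | Fact about one participant? | Bears on dosing or RNA to Day 8? |
|---|---|---|
| 7, trend bullet | No, a pattern across several | Not as worded |
| 9, oversight | No | No |
| 12, safety samples | Yes | No |
| 8, accountability not done | Possibly | Yes, if it leaves dosing undocumented |
| 4, no Visit 6 RNA | Yes | Part 2 (Day 8) yes; Part 1 (Day 11) no |

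The last row follows from SAP 7.1.1, where Visit 6 is Day 11 in Part 1, and SAP 10.1.4 and 11.1.2, which stop both models at Day 8. A Part 1 participant can be dropped for lacking a value that neither model uses.

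**Plan's own figure.** None concerns PP exclusions. The SD of 0.4 log10 and n = 6 used below come from Protocol 10.1.1. As a check on those inputs, treat the SD as known. At a true mean of 1.3, the chance that the posterior probability reaches 20% is Φ(0.8416) = 80.0%, against 81.8% in Table 5. That table rests on 1000 simulations (Monte Carlo error about 1 point). Using the stated priors and a single-arm variance, simulation gives 81.3%.

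**Arm mean.** SE = 0.4/√n; the 95% half-width is t(n−1) × SE.

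| n | SE | Half-width (log10) | SE relative to n = 6 |
|---|---|---|---|
| 6 | 0.163 | 2.571 × 0.163 = 0.42 | 1 |
| 5 | 0.179 | 2.776 × 0.179 = 0.50 | √(6/5) = 1.10 |
| 4 | 0.200 | 3.182 × 0.200 = 0.64 | √(6/4) = 1.22 |

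**Pooled model.** The SAP form is Emax/(1 + ED50/Dose), at 10, 40, 80, 140 and 200 mg with 6 each, 30 active participants in all. The gradient is g = [D/(D + ED50), −Emax·D/(D + ED50)²] and the information matrix is Σ n g gᵀ/0.4². Assume ED50 = 10 mg (Protocol 5.5.1 expects about half the maximum effect at 10 mg) and Emax = 2.0 log10:

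- all 30: SE(ED50) = 3.755 mg
- one lost per arm: 4.114, ratio 1.10
- two lost per arm: 4.599, ratio 1.22
- two lost at 10 mg only: 4.337, ratio 1.15

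Over an assumed ED50 of 5 to 20 mg, two lost at 10 mg alone raise SE(ED50) by 11% to 17%, and three lost there by 18% to 31%. The ratios are the same for Emax of 1.5.

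**The case against.** The strongest reply is that the damage is contained. ITT is the primary efficacy population, RNA summaries and modelled changes by dose are given on ITT (Tables 2.1 to 2.12), no hypothesis is tested, and the dose-response work is exploratory. Exclusions will be visible in Tables 1.6 and 1.9 and Listings 6 and 8. All of this stands and limits the point to the dose-response, exposure-response and PP sensitivity analyses. Visibility, however, does not supply the estimate without the exclusions.

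The Protocol Deviation Management Plan cited in SAP 4.1 is not available here and may map categories to participants. If so, the SAP should say so, because 13.1.1 itself gives no mapping.

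Four stronger readings are tempting, and the documents do not support them.

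- **Whole sites will be removed.** The governing sentence speaks of a participant meeting a criterion, and nothing says a site finding excludes everyone there. That is one possible reading; the fault is that the list does not settle it.
- **Placebo participants face a looser adherence rule.** Item 3 reads "Participant who have missed at least one dose of GSK3640254", but the PP definition in SAP 4 and Protocol 10.2 already requires all doses from every participant.
- **An unblinded team freely chooses exclusions.** SAP 4.1 requires deviation review before unblinding and freeze, and SAP 3.2 releases codes after freeze. Protocol 7.4 says sponsor staff may see unblinded data, names the study team's access for the interim, and otherwise keeps staff blinded. The safeguard is real but partial: Part 1, with 12 of the 30 planned active participants, has already had its unblinded interim, and this SAP reports that interim as done.
- **Missing accountability is never relevant.** Doses may be self-administered on non-clinic days (Protocol 5.1.1.2), and Protocol 7.6 ties capsule records to compliance where diaries are used. A participant whose dosing cannot be documented is a proper PP exclusion.

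**Conclusion.** The point holds for the trend bullet of item 7, item 9 and item 12. Followed as written, they can remove participants with complete dosing and RNA data from the only dose-response analysis and from exposure-response. Item 4 does the same for Part 1 participants who lack only the Day 11 value.

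The precision losses shown (10% or 22% for an arm mean; 11% to 17% for ED50 if two are lost at the lowest dose) are illustrations. They assume SD 0.4, equal arms of 6 and an ED50 of 5 to 20 mg. Site numbers and likely exclusions are not stated, so the actual loss may be nil. Any shift in the fitted curve cannot be sized from the documents. The primary ITT analysis is untouched. This should be corrected before the PP set is fixed, but it does not threaten the main result.

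**What to change.** 1. Delete the trend bullet of item 7 and items 9 and 12 from SAP 13.1.1; report them as deviations only.
2. Keep "IP accountability not done" as an exclusion only where receipt of all doses cannot be documented for that participant.
3. For the dose-response and PK/PD analyses, replace the Visit 6 requirement with the RNA needed for the analysed interval, to Day 8. Word it by samples scheduled on or before that day, since Part 1 Visit 5 may fall on Day 8, 9 or 10. SAP 4 separately requires all post-baseline RNA for PP, so the set for these two analyses needs its own line there or item 4 alone will have no effect. Protocol 10.3.3.1 names no population for this work, so the change does not conflict with it.
4. Add an ITT run of Table 5.1 as a sensitivity analysis.

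The cost is an edit to SAP 4 and 13.1.1 and one repeated output. No new data are needed.

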13.2. Appendix 2: Schedule of Activities

Study Part 1:

Procedure ¹	Treatment Period Day 1 – Day 10									Post-Dosing Follow Up Period Day 11 – 17			Final Follow-up Day 18-24	
	Day 1	Day 2	Day 3, 4 Choose one day for the Clinic Visit 3. The other day will be a virtual event.		Day 5, 6, 7 Choose one day for the Clinic Visit 4. The other days will be virtual events.			Day 8, 9, 10 Choose one day for the Clinic Visit 5. The other days will be virtual events.			Day 11	Day 12	Day 13, 14, 15, 16 or 17	Day 18, 19, 20, 21, 22, 23 or 24
	Clinic Visit 1	Clinic Visit 2	Clinic Visit 3	Virtual	Clinic Visit 4	Virtual	Virtual	Clinic Visit 5	Virtual	Virtual	Clinic Visit 6	Clinic Visit 7	Clinic Visit 8	Clinic Visit 9
Clinical Assessments														
Outpatient Visit ²	X	X	X		X			X			X	X	X	X
Video/Phone Call				X		X	X		X	X				
Verify Inclusion/ Exclusion Criteria	X													
Medical/medication/drug/alcohol history	X													
Prior Anti-retroviral (ARV) Check	X													
CDC Classification	X													X

CONFIDENTIAL

208132

Procedure ¹	Treatment Period Day 1 – Day 10									Post-Dosing Follow Up Period Day 11 – 17			Final Follow-up Day 18-24	
	Day 1	Day 2	Day 3, 4 Choose one day for the Clinic Visit 3. The other day will be a virtual event.		Day 5, 6, 7 Choose one day for the Clinic Visit 4. The other days will be virtual events.			Day 8, 9, 10 Choose one day for the Clinic Visit 5. The other days will be virtual events.			Day 11	Day 12	Day 13, 14, 15, 16 or 17	Day 18, 19, 20, 21, 22, 23 or 24
	Clinic Visit 1	Clinic Visit 2	Clinic Visit 3	Virtual	Clinic Visit 4	Virtual	Virtual	Clinic Visit 5	Virtual	Virtual	Clinic Visit 6	Clinic Visit 7	Clinic Visit 8	Clinic Visit 9
HIV-associated conditions assessments ³	X	X	X	X	X	X	X	X	X	X	X	X	X	X
Adverse event (AE)/SAE assessment ³	X	X	X	X	X	X	X	X	X	X	X	X	X	X
Concomitant medication review ³	X	X	X	X	X	X	X	X	X	X	X	X	X	X
Weight, BMI and Physical exam ⁴	X													
Vital Signs	X	X	X					X						X
C-SSRS Administration (Since Last Visit form)											X			

CONFIDENTIAL

208132

Procedure ¹	Treatment Period Day 1 – Day 10									Post-Dosing Follow Up Period Day 11 – 17			Final Follow-up Day 18-24	
	Day 1	Day 2	Day 3, 4 Choose one day for the Clinic Visit 3. The other day will be a virtual event.		Day 5, 6, 7 Choose one day for the Clinic Visit 4. The other days will be virtual events.			Day 8, 9, 10 Choose one day for the Clinic Visit 5. The other days will be virtual events.			Day 11	Day 12	Day 13, 14, 15, 16 or 17	Day 18, 19, 20, 21, 22, 23 or 24
	Clinic Visit 1	Clinic Visit 2	Clinic Visit 3	Virtual	Clinic Visit 4	Virtual	Virtual	Clinic Visit 5	Virtual	Virtual	Clinic Visit 6	Clinic Visit 7	Clinic Visit 8	Clinic Visit 9
Clinical Procedures														
12-lead ECG (triplicate reading, pre-dose; single readings at PK draws 2hr, 4hr, and 6hr)	X													
12-lead ECG (single reading, pre-dose at Visits 2 and 3)		X	X											X
12-lead ECG (single reading pre-dose and at PK draws 2hr, 4hr, and 6hr)								X						
Pharmacogenetics (PGX) Collection (if consented)	X													

CONFIDENTIAL

208132

Procedure ¹	Treatment Period Day 1 – Day 10									Post-Dosing Follow Up Period Day 11 – 17			Final Follow-up Day 18-24	
	Day 1	Day 2	Day 3, 4 Choose one day for the Clinic Visit 3. The other day will be a virtual event.		Day 5, 6, 7 Choose one day for the Clinic Visit 4. The other days will be virtual events.			Day 8, 9, 10 Choose one day for the Clinic Visit 5. The other days will be virtual events.			Day 11	Day 12	Day 13, 14, 15, 16 or 17	Day 18, 19, 20, 21, 22, 23 or 24
	Clinic Visit 1	Clinic Visit 2	Clinic Visit 3	Virtual	Clinic Visit 4	Virtual	Virtual	Clinic Visit 5	Virtual	Virtual	Clinic Visit 6	Clinic Visit 7	Clinic Visit 8	Clinic Visit 9
Hematology/Chemistry/Urine	X	X	X		X			X			X			X
Fasting Lipid Panel (approximately 8 hrs)	X										X			X
Lymphocyte T-cell subsets (CD4, CD8)	X										X			
Plasma for HIV-1 genotype/phenotype ⁵	X	X	X		X			X			X	X	X	X
Plasma for storage ⁶	X	X	X		X			X			X	X	X	X
HIV-1 RNA	X	X	X		X			X			X	X	X	X

CONFIDENTIAL

208132

Procedure ¹	Treatment Period Day 1 – Day 10									Post-Dosing Follow Up Period Day 11 – 17			Final Follow-up Day 18-24	
	Day 1	Day 2	Day 3, 4 Choose one day for the Clinic Visit 3. The other day will be a virtual event.		Day 5, 6, 7 Choose one day for the Clinic Visit 4. The other days will be virtual events.			Day 8, 9, 10 Choose one day for the Clinic Visit 5. The other days will be virtual events.			Day 11	Day 12	Day 13, 14, 15, 16 or 17	Day 18, 19, 20, 21, 22, 23 or 24
	Clinic Visit 1	Clinic Visit 2	Clinic Visit 3	Virtual	Clinic Visit 4	Virtual	Virtual	Clinic Visit 5	Virtual	Virtual	Clinic Visit 6	Clinic Visit 7	Clinic Visit 8	Clinic Visit 9
Single, Pharmacokinetic (PK) sample (pre- dose at Visits 3 and 4)			X		X						X ⁷	X	X	
Intensive PK sampling ⁸ (with sample at 24hr time point the next morning)	X							X ⁹						
Observed dosing with GSK3640254/plac ebo ³	X	X	X	X	X	X	X	X	X	X				
IWRS (RAMOS) activity ¹⁰	X													

CONFIDENTIAL

208132

1. Procedures should be performed in the following order: ECG, Vitals, Blood Draws, followed by dose administration.
 2. The study requires 9 in-clinic visits. Flexibility is offered for Visits 3, 4, 5, 8 and 9. The visit schedule for each participant should be pre-planned to be sure weekend, work schedules and clinic hours are appropriately considered. No visit interval during the treatment period can be greater than 3 days.
 3. These assessments must be conducted with a participant during each day indicated, to include the days when the participant is not in the clinic. This can be done in via phone, preferably via a visual method (as locally permitted) of Skype, Facetime, WhatsApp, et. al.
 4. Physical Exam will include, at a minimum, assessments of the Skin, Heart, Lungs, and Abdomen (liver and spleen).
 5. Genotypic/Phenotypic testing will be conducted on Day 1 and Day 11 samples, with other visits tested as appropriate.
 6. Plasma samples for storage will be collected at each visit starting at Day 1, including unscheduled visits. These samples will be used when needed, such as when samples are lost or where quantity is insufficient for testing. In the event samples are not used by study completion, they will be utilized for additional research on ARV resistance and/or HIV-1 disease biology/host immune response (excluding any human genetic testing)
 7. If the Intensive PK day occurs on Day 10, do not collect the Day 11 pre-dose PK sample (as it is redundant with the 24-hr PK collection (completing the sample set started on Day 10).
 8. Intensive Plasma PK samples will be collected as outlined in Protocol Table 4 in Section 9.5
 9. If Day 8 or 9 is the Clinic Visit 5 to include the Intensive PK collection, the participant must return the following day for the 24-hr PK collection, meal and dosing. The assessments to be done as indicated on what is a “virtual visit day” should be captured as a virtual visit, even if the questions are asked in the clinic.
 10. Log in to RAMOS on Day 1 to randomize the participant and to receive blinded study treatment. Subsequently log-in to RAMOS for study treatment supply as needed. If a participant is discontinued from the study early, log in to RAMOS to record the discontinuation.
- The timing and number of planned study assessments, including safety, efficacy, pharmacokinetic, pharmacodynamic/biomarker assessments may be altered during the course of the study based on newly available data (e.g., to obtain data closer to the time of peak plasma concentrations) to ensure appropriate monitoring.
 - Any changes in the timing or addition of time points for any planned study assessments must be documented and approved by the relevant study team member and then archived in the sponsor and site study files, but will not constitute a protocol amendment. The IRB/IEC will be informed of any safety issues that require alteration of the safety monitoring scheme or amendment of the ICF.

CONFIDENTIAL

208132

Study Part 2:

Procedure ¹	Treatment Period Day 1 – Day 7						Post-Dosing Follow Up Period	Final Follow- up	
	Day 1	Day 2	Day 3, 4 Choose one day for the Clinic Visit 3. The other day will be a virtual event.		Day 5, 6 Choose one day for the Clinic Visit 4. The other day will be a virtual event.		Day 7	Day 8	Day 10, 11 or 12
	Clinic Visit 1	Clinic Visit 2	Clinic Visit 3	Virtual	Clinic Visit 4	Virtual	Clinic Visit 5	Clinic Visit 6	Clinic Visit 7
Clinical Assessments									
Outpatient Visit ²	X	X	X		X		X	X	X
Video/Phone Call				X		X			
Verify Inclusion/ Exclusion Criteria	X								
Medical/medicatio n/drug/alcohol history	X								
Prior Anti-retroviral (ARV) Check	X								
CDC Classification	X								X

CONFIDENTIAL

208132

Procedure ¹	Treatment Period Day 1 – Day 7						Post-Dosing Follow Up Period	Final Follow- up	
	Day 1	Day 2	Day 3, 4 Choose one day for the Clinic Visit 3. The other day will be a virtual event.		Day 5, 6 Choose one day for the Clinic Visit 4. The other day will be a virtual event.		Day 7	Day 8	Day 10, 11 or 12
	Clinic Visit 1	Clinic Visit 2	Clinic Visit 3	Virtual	Clinic Visit 4	Virtual	Clinic Visit 5	Clinic Visit 6	Clinic Visit 7
HIV-associated conditions assessments ³	X	X	X	X	X	X	X	X	X
Adverse event (AE)/SAE assessment ³	X	X	X	X	X	X	X	X	X
Concomitant medication review ³	X	X	X	X	X	X	X	X	X
Weight, BMI and Physical exam ⁴	X								
Vital Signs	X	X	X				X		X
C-SSRS Administration (Since Last Visit form)								X	

CONFIDENTIAL

208132

Procedure ¹	Treatment Period Day 1 – Day 7						Post-Dosing Follow Up Period	Final Follow- up	
	Day 1	Day 2	Day 3, 4 Choose one day for the Clinic Visit 3. The other day will be a virtual event.		Day 5, 6 Choose one day for the Clinic Visit 4. The other day will be a virtual event.		Day 7	Day 8	Day 10, 11 or 12
	Clinic Visit 1	Clinic Visit 2	Clinic Visit 3	Virtual	Clinic Visit 4	Virtual	Clinic Visit 5	Clinic Visit 6	Clinic Visit 7
Clinical Procedures									
12-lead ECG (triplicate reading, done pre-dose; single readings at PK draws 2hr, 4hr, and 6hr)	X								
12-lead ECG (single reading, done pre-dose at Visits 2 and 3)		X	X						X
12-lead ECG (single reading done pre-dose and at PK draws 2hr, 4hr, and 6hr)							X		

CONFIDENTIAL

208132

Procedure ¹	Treatment Period Day 1 – Day 7						Post-Dosing Follow Up Period	Final Follow- up	
	Day 1	Day 2	Day 3, 4 Choose one day for the Clinic Visit 3. The other day will be a virtual event.		Day 5, 6 Choose one day for the Clinic Visit 4. The other day will be a virtual event.		Day 7	Day 8	Day 10, 11 or 12
	Clinic Visit 1	Clinic Visit 2	Clinic Visit 3	Virtual	Clinic Visit 4	Virtual	Clinic Visit 5	Clinic Visit 6	Clinic Visit 7
Pharmacogenetics (PGX) Collection (if consented)	X								
Hematology/Chem istry/Urine	X	X	X		X		X	X	X
Fasting Lipid Panel (approximately 8 hrs)	X							X	X
Lymphocyte T-cell subsets (CD4, CD8)	X							X	
Plasma for HIV-1 genotype/phenoty pe ⁵	X	X	X		X		X	X	
Plasma for storage ⁶	X	X	X		X		X	X	X

CONFIDENTIAL

208132

Procedure ¹	Treatment Period Day 1 – Day 7						Post-Dosing Follow Up Period	Final Follow- up	
	Day 1	Day 2	Day 3, 4 Choose one day for the Clinic Visit 3. The other day will be a virtual event.		Day 5, 6 Choose one day for the Clinic Visit 4. The other day will be a virtual event.		Day 7	Day 8	Day 10, 11 or 12
	Clinic Visit 1	Clinic Visit 2	Clinic Visit 3	Virtual	Clinic Visit 4	Virtual	Clinic Visit 5	Clinic Visit 6	Clinic Visit 7
HIV-1 RNA	X	X	X		X		X	X	X
Single, Pharmacokinetic (PK) sample done pre-dose			X		X				
Intensive PK sampling (to include the 24hr samples drawn the next day)	X						X		
Observed dosing with GSK3640254 /placebo ³	X	X	X	X	X	X	X		

CONFIDENTIAL

208132

Procedure ¹	Treatment Period Day 1 – Day 7						Post-Dosing Follow Up Period	Final Follow- up	
	Day 1	Day 2	Day 3, 4 Choose one day for the Clinic Visit 3. The other day will be a virtual event.		Day 5, 6 Choose one day for the Clinic Visit 4. The other day will be a virtual event.		Day 7	Day 8	Day 10, 11 or 12
	Clinic Visit 1	Clinic Visit 2	Clinic Visit 3	Virtual	Clinic Visit 4	Virtual	Clinic Visit 5	Clinic Visit 6	Clinic Visit 7
Observed dosing with Investigator-selected, prescribed and provided CART, and eCRF completion								X	
IWRS (RAMOS) activity ⁸	X								

CONFIDENTIAL

208132

1. Procedures should be performed in the following order: ECG, Vitals, Blood Draws, followed by dose administration.
 2. The study requires 7 in-clinic visits. Flexibility is offered for Visits 3, 4 and 7. The visit schedule for each participant should be pre-planned to be sure weekend, work schedules and clinic hours are appropriately considered. No visit interval during the treatment period can be greater than 3 days.
 3. These assessments must be conducted with a participant during each day indicated, to include the days when the participant is not in the clinic. This can be done in via phone, preferably via a visual method (as locally permitted) of Skype, Facetime, WhatsApp, et. al.
 4. Physical Exam will include, at a minimum, assessments of the Skin, Heart, Lungs, and Abdomen (liver and spleen).
 5. Genotypic/Phenotypic testing will be conducted on Day 1 and Day 8 samples, with other visits tested as appropriate.
 6. Plasma samples for storage will be collected at each visit starting at Day 1, including unscheduled visits. These samples will be used when needed, such as when samples are lost or where quantity is insufficient for testing. In the event samples are not used by study completion, they will be utilized for additional research on ARV resistance and/or HIV-1 disease biology/host immune response (excluding any human genetic testing)
 7. Intensive Plasma PK samples will be collected as outlined in Protocol Table 4 in Section 9.5
 8. Log in to RAMOS on Day 1 to dispense blinded study treatment. Subsequently log-in to RAMOS for study treatment supply as needed. If a participant is discontinued from the study early, log in to RAMOS to record the discontinuation.
- The timing and number of planned study assessments, including safety, efficacy, pharmacokinetic, pharmacodynamic/biomarker assessments may be altered during the course of the study based on newly available data (e.g., to obtain data closer to the time of peak plasma concentrations) to ensure appropriate monitoring.
 - Any changes in the timing or addition of time points for any planned study assessments must be documented and approved by the relevant study team member and then archived in the sponsor and site study files but will not constitute a protocol amendment. The IRB/IEC will be informed of any safety issues that require alteration of the safety monitoring scheme or amendment of the ICF

CONFIDENTIAL

208132

